7.3.9.1 Restricted Medications

All analgesics other than acetaminophen/paracetamol are prohibited during the study. This includes, but is not restricted to, NSAIDs, opioids and topical agents for treatment of osteoarthritis of index ankle. Topical corticosteroids are allowed at any other site other than the index ankle. The analgesic medication use will be monitored at each subject assessment through review of the subject diary.

7.3.9.2 Rescue Medications

Acetaminophen/paracetamol (up to a maximum of 4.0 grams per day per the package insert or as per regional limitations) will be allowed as the rescue medication for the treatment of Osteoarthritis in the index ankle for the duration of the study. At least forty-eight hours prior to the Baseline Visit, 1, 3 and 6 Month Assessments the subject should discontinue use of the rescue medication.

The subject should be instructed to track pill usage daily to convey accurate pill counts at follow-up assessments.

7.3.9.3 Concomitant Medications

A medication is considered concomitant if taken after signing the ICF and up to and including the last follow-up assessment. Data on medications will include: medication name, dose, unit, route, frequency, start date, stop date, indication and whether the medication was taken for an AE.

At each study assessment, the subject will be asked about any new medications that were started since the last assessment. Indications for any new medications started after the study treatment will be recorded as AEs, unless the medications are administered for a pre-existing condition.

7.3.9.4 Non-Drug Therapies

Non-drug therapies are any therapies used to treat the index ankle that are not a pharmaceutical

treatments.

- 7.3.9.5 Joint Function Assessment Subjects will receive assessment of the respective joints for functional use.
- 7.3.9.6 Subject Diary
 Subjects will receive diary for to record rescue medications and concomitant medications.

7.4 Baseline Visit: Treatment Visit (Day 0)

The Baseline Visit (Day 0) will occur 7 to 14 days after the Screening Visit to allow for rescue medication washout. The injection will occur at this Baseline visit along with the following activities:

Before Treatment Injection

- Concomitant Medications
- Current non-drug therapies
- Confirm Medication Washout
 - If subject did not complete medications washout, reschedule the visit to allow washout to be completed.
- Patient Global Assessment (PGA)
- AOFAS index
- Index & Contralateral Hip, Knee and Ankle Joint Pain on Walking (NRS Scale)
 - o Confirm the Baseline Inclusion & Exclusion criteria for NRS Pain on Walking
- Physical Exam of Index and Contralateral Hip, Knee and Ankle Joints

Treatment Procedure

The Treating Physician may perform the Study Injection to the index ankle as standard of care dictates or delegate the injection to qualified study staff.

Intra-articular injection of the index ankle joint may be conducted under fluoroscopic or ultrasound guidance as required by standard of care treatment. Guidelines for the injection procedural steps are provided below. Modifications to this technique should be recorded in the CRFs.

- Patient is supine.
- Prep the skin at injection site with 1% betadine solution or equivalent.
- Peri- articular injection site anesthesia of lidocaine or topical refrigerant anesthetic (e.g. ethyl chloride) may be utilized.
- The ankle is dorsiflexed to a neutral position. Injection site is located in the anteromedial portal of the ankle joint as described for ankle arthroscopy
- Fluoroscopic or ultrasound guidance may be utilized if required to insert 18-21 gauge needle. Traction can be applied if required to gain access.
- Insert needle until resistance against the articular surface and then withdraw the needle 1-2 mm.
- If using fluoroscopic guidance, a small amount of fluoroscopic contrast agent (0.5 to 1.0 ml) should be injected through the needle to verify intra-articular placement.
- If using ultrasound guidance, a small volume of air (up to 0.5 ml) may be injected to verify IA

positioning.

- If pooling of the contrast agent or air around the needle tip is observed, the needle should be repositioned.
- When contrast agent or air is successfully injected into the joint, intra-articular placement is confirmed.
- Following confirmation of intra-articular needle placement, the joint may be aspirated to remove synovial fluid.
 - Confirm the Baseline Exclusion for synovial aspirate.
- 2 ml of CINGAL is injected into the joint.
- Intra-articular anesthetic should NOT be administered as part of the injection procedure.
- Following the injection, the patient should be advised to maintain a low level of physical activity for the next 48 hours. Cold therapy and/or acetaminophen/ paracetamol may be prescribed to address short term injection site pain.

Post-Treatment Assessments and Instructions

Prior to leaving the clinic, the subject should be evaluated for local and non-local AEs. All post-treatment signs and symptoms that are unexpected should be recorded as AEs. The expected appearance of the index ankle should be discussed with the subject with a request that all unexpected symptoms be reported to a member of the study team.

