6.3 Exploratory Endpoints

Any comparisons across timepoints (baseline to 6 months) not described in the primary or secondary endpoints, including but not limited to:

- Demographics
- Medical History
- History of joint osteoarthritis
- Rescue Medication Use
- Treatment Failure
- Injection procedure
- Concomitant medications
- Non-drug therapy.

6.4 Safety Endpoint:

The incidence, severity, and relationship to treatment of all Adverse Events (AE) will be collected from the treatment injection to the 6-month assessment.

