8. SAFETY PROCESSES

Safety of the subjects participating in this clinical investigation will be monitored throughout the clinical investigation using the Adverse Event (AE) reporting process in the EDC system, to identify real and potential safety issues.

Adverse events will be reported according to the ISO 14155:2011, while recognizing and following the requirements including reporting timelines specified in other specific laws, regulations, directives, standards and/or guidelines as appropriate and as required by the countries in which the study is conducted.

All AEs that occur during or after injection will be recorded. Worsening of a condition that existed prior to the study injection should be recorded as an AE. At each assessment during the trial, AEs that have occurred since the previous assessment must be recorded. All subjects will be questioned and evaluated for AEs or complications associated with the procedure. Complications of the injection include, but are not necessarily limited to: pain, swelling, erythema, bleeding and/or infection at the injection site. The Investigator will determine the severity and relationship of each event, as defined above.

AEs observed during the course of this study, regardless of severity or relationship to the device and/or the procedure will be recorded on the CRF. Each reported complication/AE will also include the duration, action taken to address the AE, and the resolution status (e.g. ongoing, resolved). These subjects will continue to be evaluated for safety at all scheduled follow-up points.

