8.2 Safety Reporting Process – principal investigator responsibilities

The principal investigator shall report all adverse events and device deficiencies in the appropriate sections of the e-CRF and provide where requested by the sponsor, the necessary clinical or technical information that may contribute to clarifying the circumstances.

The principal investigator shall report all serious adverse events (SAEs) and device deficiencies (DDs) that might have led to a SAE: if a) suitable action had not been taken or b) intervention had not been made or c) if circumstances had been less fortunate, to the sponsor within 24 hours after knowledge of the event using the appropriate e-CRF.

When required by national or local regulations, the principal investigator shall also notify the EC/IRB and Regulatory Agencies of all reportable events according to national regulations within the by regulations required timelines and may also be requested by the EC/IRBs to provide annual reports. The principal investigator shall document all adverse events and device deficiencies in the e-CRF from the point of enrollment until the subject is exited from the study.

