9.2.2 Adverse Events

Subjects with AEs will be summarized with frequencies and percentages by system organ class and preferred term, severity, and relationship to investigational product/procedure. In summaries of AEs by severity and relationship to investigational product/procedure, subjects reporting multiple episodes will be counted once under the worst severity and the strongest relationship, respectively. Serious Adverse Events will also be presented by relationship to investigational product/procedure.

Adverse events occurring prior to the index treatment will not be recorded in this trial.

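### Section 7.4 asks for unexpected post-injection signs to be recorded, which conflicts with the all-AE rule in sections 6.4 and 8 and may leave expected injection-site reactions unrecorded

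*Protocol*

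**What the plan says.** Protocol section 7.4, under the post-treatment assessments and instructions, contains three relevant statements. Before leaving the clinic, "the subject should be evaluated for local and non-local AEs". Then comes the recording rule: "All post-treatment signs and symptoms that are unexpected should be recorded as AEs". Last, staff discuss with the subject how the ankle is expected to look, "with a request that all unexpected symptoms be reported to a member of the study team".

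The other safety passages carry no such qualifier. Section 8 states: "All AEs that occur during or after injection will be recorded". It applies this whatever the severity or relationship, and adds: "Complications of the injection include, but are not necessarily limited to: pain, swelling, erythema, bleeding and/or infection at the injection site". The safety endpoint in section 6.4 reads: "The incidence, severity, and relationship to treatment of all Adverse Events (AE) will be collected from the treatment injection to the 6-month assessment". SAP section 3.0 repeats that endpoint, and SAP section 4.4 plans counts of local injection-site events against non-local events.

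On when collection starts, section 8.2 has the investigator document events "from the point of enrollment until the subject is exited from the study", while section 9.2.2 says: "Adverse events occurring prior to the index treatment will not be recorded in this trial".

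**The concern.** The qualifier *unexpected* in section 7.4 does work only if expected signs are handled differently, and the natural difference is that they are not entered as adverse events. The reactions most likely to be called expected are those the product and the needle are known to cause: pain, swelling and redness at the injection site. They are also the events section 8 names, and the ones the SAP's local versus non-local table is meant to count.

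Safety is part of the stated goal (Protocol section 3), in an open-label study of 25 subjects with no comparator. A recording rule that drops expected local reactions lowers the reported rate in the product's favour. Up to 10 sites may also draw the line in different places. Events never entered cannot be recovered at the analysis stage.

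**Working it through.** The plan gives no figure on this point, so the check is a comparison of the passages followed by an illustration of size.

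**1. The rules side by side**

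| Place | What is to be recorded or reported | Expectedness filter |
|---|---|---|
| 7.4, evaluation before discharge | local and non-local AEs | none |
| 7.4, recording sentence | post-treatment signs and symptoms | unexpected ones |
| 7.4, request to the subject | symptoms | unexpected ones |
| 6.4, safety endpoint | all AEs, injection to 6 months | none |
| 8, recording rule | all AEs during or after injection | none |
| 8.1, AE definition | any untoward occurrence, procedure-related included | none |

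Two sentences of 7.4 stand apart from the rest. The protocol does not define *unexpected* for this purpose. Its nearest concept, anticipated against unanticipated in section 8.1, concerns serious device effects and refers to the risk analysis report.

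**2. What a site would call expected.** Section 4.2 lists temporary injection-site pain, swelling and tenderness among the risks of any ankle injection. It classes local steroid reactions as common. It also anticipates that the event profile seen in the knee will carry over to the ankle. Section 7.4 itself foresees short-term pain at the injection site. A site applying the 7.4 wording to these reactions has the protocol's own support for calling them expected.

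**3. What else could capture a transient reaction**

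- *Evaluation before discharge (7.4).* Catches what appears in the clinic, but not what starts at home.
- *Questioning at each assessment (8, 7.6).* The first scheduled visit after injection is Month 1 (7.1), so this rests on recall after about a month.
- *Subject diary (7.3.9.6).* Holds rescue and concomitant medications, not symptoms.
- *New medication rule (7.3.9.3).* Turns the indication for a newly started drug into an AE, but paracetamol is already the permitted rescue drug (7.3.9.2) and may not count as new.
- *Spontaneous report by the subject.* This is the route that 7.4 narrows.

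**4. Size.** Let p be the true share of subjects with a local reaction and f the share of those left unrecorded because they were judged expected. The documents give neither, so both are assumptions. With 25 treated (synopsis; Protocol 9.1):

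- subjects with a reaction = 25 × p
- subjects recorded = 25 × p × (1 − f)
- chance of recording at least one = 1 − [1 − p(1 − f)]^25

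| p | With a reaction | Recorded, f = 0 | Recorded, f = 50% | Recorded, f = 100% | Chance of at least one, f = 0 | Chance of at least one, f = 50% |
|---|---|---|---|---|---|---|
| 5% | 1.25 | 1.25 | 0.63 | 0 | 72% | 47% |
| 10% | 2.5 | 2.5 | 1.25 | 0 | 93% | 72% |
| 20% | 5 | 5 | 2.5 | 0 | 99.6% | 93% |

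For example, with p = 10% and f = 50%: 25 × 0.10 × 0.50 = 1.25, and 1 − 0.95^25 = 0.72.

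The only frequency in the documents is the common class in 4.2, from 1% to under 10%. That is 25 × 0.01 = 0.25 to just under 25 × 0.10 = 2.5 subjects. It describes a bundle of local reactions to the steroid component, sterile abscess and necrosis included, and is not an ankle rate for Cingal.

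**5. Start of collection.** Section 8.2 starts at enrollment, which is not defined. Section 7.3.1 places consent before enrollment. Section 6.6 includes the baseline criteria among the enrollment criteria, and the last of these is checked just before the injection. If enrollment happens at screening, 8.2 and 9.2.2 cannot both be followed in the 7 to 14 days before baseline (7.4). If it is completed on Day 0, the conflict nearly disappears. Sections 6.4 and 8 and the schedule in 7.1, which has no AE assessment at screening, agree with 9.2.2.

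**The case against.** The strongest reply is that section 7.4 never says *only*. It asks for unexpected signs to be recorded and does not forbid recording others, and the sentence before it asks for an unfiltered evaluation of local and non-local events. Section 8 is the governing safety section and states the all-AE rule. Sections 8.2 and 13.6 have the investigator report all AEs, subjects are questioned at every assessment, and the SAP's local versus non-local table shows that such events are meant to be recorded.

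Most of this stands. It rules out the inference that the safety endpoint will undercount injection reactions, or that the reported rate would be near zero. A near-zero rate would need every site to read 7.4 as exclusive, disregard section 8 and judge every reaction expected, and nothing in the documents says sites will do that.

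It does not remove the conflict. Staff on injection day work from 7.4, and the other routes are weak for a reaction that starts at home and settles within days.

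A reader might also link the 8.2 and 9.2.2 difference to missed injection reactions. It cannot cause them, because events before the injection are not injection reactions and fall outside the 6.4 window. Nor do the documents support a start at consent: 8.2 says enrollment, and 7.3.1 treats consent as a separate, earlier step.

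**Conclusion.** The conflict between 7.4 and sections 6.4 and 8 is real. Section 7.4 can be read as excluding expected reactions, and if sites read it that way, transient injection-site reactions may go unrecorded, in the direction that favours the product. The size cannot be fixed from the documents. It runs from zero, if sites follow section 8, to loss of every reaction judged expected, if 7.4 is taken as exclusive. The conclusion rests on the protocol's own listing of these reactions as known effects, the Month 1 first visit and the medication-only diary.

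The difference between 8.2 and 9.2.2 is a separate and minor inconsistency. It is real only if enrollment comes before the injection, and it does not affect the safety endpoint.

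**What to change.** In section 7.4, delete the qualifier in both sentences, so that all post-treatment signs and symptoms are recorded as AEs and subjects are asked to report all symptoms. If the sponsor wants to separate known reactions from others, add an expected/unexpected flag to the AE form and keep the distinction out of the recording rule.

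Separately, define the point of enrollment and state one start point for AE collection in 8.2 and 9.2.2. The 6.4 endpoint window, injection to 6 months, stays as it is.

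The cost is a few words through the amendment route in section 13.3, a reminder to sites, and an extra form field if the flag is used. More mild local events may be entered, so the reported local rate may be somewhat higher.

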7.5 Follow-Up Visits

All study subjects will have follow-up visits at 1, 3 and 6 Months after Baseline to evaluate the joint pain score and to assess adverse events.

The subject should be contacted at least 48 hours prior to their scheduled assessments to be reminded of the required assessment (and applicable wash out period) and to schedule the date and time of contact. At least three documented attempts will be made to contact the subject in order to accomplish maximum subject compliance with the follow-up schedule.

The following tests will be performed at the follow-up visits at 1, 3, and 6 months.

7.6 Follow-up Visits (± 7 days)

- Assess Concomitant Medications
- Assess Non- drug therapies
- Assessment of Adverse Events
- Confirm Rescue Medication Washout
 - If subject did not complete medications washout, reschedule the visit to allow washout to be completed.
- Assess Rescue Medication usage
- Collect and assess subject diary

- Patient Global Assessment (PGA)
- AOFAS index and contralateral joints
- Index & Contralateral Hip, Knee and Ankle Joint Pain on walking (NRS)
- Physical Exam of Index and Contralateral Hip, Knee and Ankle Joints

8. SAFETY PROCESSES

Safety of the subjects participating in this clinical investigation will be monitored throughout the clinical investigation using the Adverse Event (AE) reporting process in the EDC system, to identify real and potential safety issues.

Adverse events will be reported according to the ISO 14155:2011, while recognizing and following the requirements including reporting timelines specified in other specific laws, regulations, directives, standards and/or guidelines as appropriate and as required by the countries in which the study is conducted.

All AEs that occur during or after injection will be recorded. Worsening of a condition that existed prior to the study injection should be recorded as an AE. At each assessment during the trial, AEs that have occurred since the previous assessment must be recorded. All subjects will be questioned and evaluated for AEs or complications associated with the procedure. Complications of the injection include, but are not necessarily limited to: pain, swelling, erythema, bleeding and/or infection at the injection site. The Investigator will determine the severity and relationship of each event, as defined above.

AEs observed during the course of this study, regardless of severity or relationship to the device and/or the procedure will be recorded on the CRF. Each reported complication/AE will also include the duration, action taken to address the AE, and the resolution status (e.g. ongoing, resolved). These subjects will continue to be evaluated for safety at all scheduled follow-up points.

8.1 Definition of Adverse Events

Adverse Device Effect (ADE)

Adverse event related to the use of an investigational medical device.

Note 1: This definition includes adverse events resulting from insufficient or inadequate instructions for use, deployment, implantation, installation, operation, or any malfunction of the investigational medical device.

Note 2: This definition includes any event resulting from the use error or intentional misuse of the investigational medical device.

Adverse Event (AE)

Any untoward medical occurrence, unintended disease or injury or untoward clinical signs (including an abnormal laboratory finding) in subjects, users or other persons whether or not related to the investigational medical device.

Note 1: This includes events related to the investigational medical device or the comparator.

Note 2: This includes events related to the procedures involved.

Note 3: For users or other persons this is restricted to events related to the investigational medical device.

Device Deficiencies (DD)

The inadequacy of a medical device with respect to its identity, quality, durability, reliability, safety or performance.

Note: Device deficiencies include malfunctions, use errors, and inadequate labeling.

Device deficiencies that did not lead to an adverse event but could have led to a medical occurrence

- a) if either suitable action had not been taken,
- b) if intervention had not been made, or
- c) if circumstances had been less fortunate,

shall be reported under the same conditions as a serious adverse event.

Malfunction

Failure of an investigational medical device to perform in accordance with its intended purpose when used in accordance with the instructions for use or Clinical Investigation Plan.

Serious Adverse Events (SAE)

An adverse event that:

- a) led to a death,
- b) led to a serious deterioration in the health of the subject user or other persons that either resulted in:
 - 1) a life-threatening illness or injury, or
 - 2) a permanent impairment of a body structure or a body function, or
 - 3) in-patient or prolonged hospitalization. or
 - 4) medical or surgical intervention to prevent life threatening illness or injury or permanent impairment to a body structure or a body function.
- c) led to foetal distress, foetal death or a congenital abnormality or birth defect

Note: A planned hospitalization for pre-existing condition or a procedure required by the protocol without a serious deterioration in health is not considered to be a serious adverse event.

Serious Adverse Device Effects (SADE)

An Adverse Device Effect that has resulted in any of the consequences characteristic of a serious adverse event.

Anticipated Serious Adverse Device Effect (ASADE) is an effect which by its nature, incidence, severity or outcome has been identified in the risk analysis report.

Unanticipated Serious Adverse Device Effects (USADE)

A Serious Adverse Device Effect which by its nature, incidence, severity or outcome has not been identified in the current version of the risk analysis report.

